#### **4.1.7 PD-1 blockade in Head and Neck cancer (HNSCC)**

PD-1 blockade was shown to be effective in HNSCC with a response rate of **16-18%** as reported recent in the Keynote 12 study (*Seiwert Lancet Oncology 2016, Chow et al JCO 2016*), with an estimated median overall survival of ~10-12months despite a heavily pretreated population (~60% of patients had 2 or more prior lines of therapy) compared to a

median overall survival of 10.1 months using the EXTREME regimen (platinum/5-FU/cetuximab) in first-line recurrent/metastatic HNSCC in a much more favorable first line population (*Vermorken NEJM 2008*).

Based on the Keynote 12 data Pembrolizumab received accelerated FDA approval as of August 5th 2016 by the FDA in the US.

Furthermore, evidence of long-term survival is seen in ~40% of patients (*Chow et al ESMO 2014*). However, a number of patients were also observed to eventually develop **acquired resistance** and some of those tumors with acquired resistance were biopsied and analysis is ongoing.

**➔ *Despite the prominent inflamed phenotype with widespread TIL infiltration and PD-L1 expression, HNSCC shows a lower rate of benefit from PD-1 blockade than melanoma, and acquired resistance/suboptimal benefit/treatment responses are prominent problems.***

Please refer to the Investigator's Brochure for additional Preclinical and Clinical data.

#### **4.1.8 Preclinical and Clinical Study Data**

Refer to the current Investigator's Brochures for additional details regarding pembrolizumab and epacadostat (iIB) for preclinical and clinical study data.

#### **4.1.9 Ongoing Clinical Studies**

Refer to the Investigator's Brochures (IBs) for pembrolizumab and epacadostat for preclinical and clinical study data.

## 4.2 Rationale

### 4.2.1 Rationale for combining PD-1 blockade with IDO inhibition in HNSCC.

IDO1 is a negative regulatory mechanism that contributes to tumor-derived immune suppression. In preclinical models, IDO1 inhibition has been shown to synergize with blockade of anti-PD-1/PD-L1 in delaying tumor growth and increasing OS (*Holmgaard 2013, Spranger 2013*). This effect was shown to be T-cell dependent, leading to enhanced T-cell proliferation and interleukin-2 production within the tumor and to a **marked increase in the effector-to-regulatory T cell ratios in the tumors**.

Epacadostat represents a novel, potent, and selective inhibitor of the enzyme indoleamine 2,3 dioxygenase 1 (IDO1) in both human tumor cells and human dendritic cells (DCs). For a thorough discussion of the pharmacology of epacadostat, refer to the epacadostat Investigator's Brochure ([iIB](#)).

While the majority of such patients with HNC can be treated with curative intent using multimodality approaches, a significant fraction of patients will fail therapy (typically within 12-18 months), especially those patients with high risk features such as advanced/bulky nodal stage, non-response to induction chemotherapy, residual disease on salvage surgery, and HPV-negative status.

HNSCC shows some of the highest levels of a CD3+/8+ lymphocyte infiltration (TILs), and T-cell inflammation, and multiple immune escape mechanisms are present (*Saloura/Seiwert, ASCO 2014, Lyford-Pike 2013*). PD-L1 expression is prominent in up to 70% of tumors, and similarly to other cancer type (*Powderly 2013*) correlates with response in the Keynote 12 study (*Seiwert, ASCO 2014/2015*) as well as a smaller cohort using the anti-PD-L1 antibody MEDI4636 (*Gibson ASCO 2015*).

Since pembrolizumab has shown significant single agent activity in HNC with a response rate of 16-18% (*Seiwert Lancet Oncology 2016; Chow JCO 2016*), excellent tolerability, and potentially affords long-term survival in a fraction of patients, further study of pembrolizumab, in particular combination aimed at overcoming acquired resistance or suboptimal benefit are indicated and clinically relevant.

### 4.2.2 Rationale for Dose Selection/Regimen/Modification

#### 4.2.2.1 Justification of Treatment Regimen

The dose selected for epacadostat for the current study was formed on the basis of having a well-tolerated safety profile as monotherapy and in combination with pembrolizumab, a robust objective response rate, durable disease control rates, as well as providing optimal target inhibition of IDO1 based on nonclinical models. Doses of epacadostat of up to 700 mg BID as monotherapy have been well tolerated and doses of 25 mg BID to 300 mg BID in combination with pembrolizumab, nivolumab, durvalumab and atezolizumab are currently being evaluated in several ongoing Phase 2 studies. Doses of pembrolizumab 2 mg/kg and 200 mg flat dose have been studied in the ongoing Phase 1/2

study of pembrolizumab in combination with epacadostat. Reductions in tumor burden were seen in 15 of 19 evaluable subjects across doses of 25 mg BID to 100 mg BID in combination with pembrolizumab 2 mg/kg and 200 mg flat dosing. Objective responses were observed in all tumor types and all are ongoing and this combination has been well tolerated.

Based on a pharmacokinetic-pharmacodynamic model for epacadostat, nearly all patients'  $C_{avg}$  exceeded the  $IC_{50}$ , the range of active drug exposure seen in non-clinical models; further dose of 100 mg BID and above exceeded the  $IC_{50}$  at trough in nearly all patients [52].

The safety profile for the 300mg bid dose of epacadostat in combination with pembrolizumab in our Phase I/II study (INCB24360-202) did not exceed the MTD in that study. While there was a higher incidence of grade 3 rash in the 300mg bid cohort compared to the 100mg bid cohort, these did not qualify as protocol-specified DLTs. The dose of 300mg epacadostat in combination with pembrolizumab is currently under study in all of Incyte's current protocols.

The dose combination of 100mg bid epacadostat plus pembrolizumab for our Phase III melanoma study (INCB24360-301) is based upon a benefit/risk assessment made specifically in melanoma in collaboration with Merck. In INCB24360-202, there was evidence of improved efficacy in melanoma subjects at all doses of epacadostat of from 50 to 300mg bid. Given that melanoma is an immunotherapy responsive tumor, and lower doses of epacadostat appeared to have similar activity, the decision was made to take the 100mg bid dose combination forward because of the lower incidence of dose interruptions and dose reductions compared to the 300mg bid dose.

However, in other tumor types, which appear to demonstrate more resistance to known immunotherapies, Incyte believes that greater target coverage for inhibition of IDO1 may be necessary. Our PK/PD modelling suggests that doses of 100mg bid epacadostat achieve an average  $IC_{50}$  at trough in most patients. At 300mg bid, epacadostat achieves target inhibition above the  $IC_{90}$  at trough. Incyte believes that greater target inhibition may be necessary in more resistant tumors, and potentially balances benefit/risk in favor of the higher epacadostat dose combination given that the dose does not exceed the MTD.

Based on observed systemic exposures and a pharmacokinetic-pharmacodynamic model for epacadostat, all patients who received 100 mg BID epacadostat in combination with pembrolizumab had time-averaged inhibition of IDO1 activity exceeding 50%, a level of PD activity associated with inhibition of tumor growth seen in non-clinical models. Dosing of 100 mg BID and above exceeded the  $IC_{50}$  at trough in nearly all patients [52]; further, the majority of patients had trough epacadostat exposures that were above the  $IC_{50}$  of IDO1 inhibition. Therefore, 100 mg BID was selected as the recommended Phase 2 dose for epacadostat in study INCB 24360-202 because this regimen had better tolerability as demonstrated by the Phase 1 safety data including fewer dose modifications (suspension and reductions) and resulted in consistent inhibition of IDO1. The overall experience of the epacadostat 100 mg BID dose in combination with pembrolizumab in study INCB 24360-202 supports this dose selected for the Phase 3 study INCB 24360-301.

#### **4.2.2.2 Rationale for a fixed dose of Pembrolizumab**

The dose of pembrolizumab planned to be studied in this study is 200 mg every 3 weeks (Q3W). The dose recently approved in the United States for treatment of melanoma subjects is 2 mg/kg Q3W. Information on the rationale for selecting 200 mg Q3W is summarized below.

An open-label Phase I study (Keynote 001) is being conducted to evaluate the safety and clinical activity of single agent pembrolizumab. The dose escalation portion of this study evaluated three dose levels, 1 mg/kg, 3 mg/kg, and 10 mg/kg, administered every 2 weeks (Q2W) and dose expansion cohort evaluated 2 mg/kg Q3W and 10 mg/kg Q3W in subjects with advanced solid tumors. All dose levels were well tolerated and no dose-limiting toxicities were observed. This first in human study of pembrolizumab showed evidence of target engagement and objective evidence of tumor size reduction at all dose levels. No MTD has been identified.

In Keynote 001, two randomized cohort evaluations (Cohorts B2 and D) of melanoma subjects receiving pembrolizumab at a dose of 2 mg/kg Q3W versus 10 mg/kg Q3W have been completed, and one randomized Cohort (Cohort B3) evaluating 10 mg/kg Q3W versus 10 mg/kg Q2W has also been completed. The clinical efficacy and safety data demonstrate a lack of clinically important differences in efficacy or safety profile at these doses. For example, in Cohort B2, advanced melanoma subjects who had received prior ipilimumab therapy were randomized to receive pembrolizumab at 2 mg/kg Q3W versus 10 mg/kg Q3W, and the objective response rate (ORR) was 28% (22/79) in the 2 mg/kg Q3W group and 28% (21/76) in the 10 mg/kg Q3W group (per RECIST 1.1 by independent central review). The proportion of subjects with drug-related adverse events (AEs), Grade 3-5 drug-related AEs, serious drug-related AEs, death or discontinuation due to an AE was comparable between groups. Cohort D which compared 2 mg/kg Q3W versus 10 mg/kg Q3W in advanced melanoma subjects naïve to ipilimumab also demonstrated overall similarity in efficacy and safety profile between two doses. In Cohort B3, advanced melanoma subjects (irrespective of prior ipilimumab therapy) were randomized to receive pembrolizumab at 10 mg/kg Q2W versus 10 mg/kg Q3W. The results demonstrate that the ORR was 35.0% (41/117) in the 10mg/kg Q2W group and 30.8% (33/107) in the 10 mg/kg Q3W group (per RECIST 1.1 by independent central review) (cut-off date of 18-April-2014). The proportion of subjects with drug-related AEs, Grade 3-5 drug-related AEs, serious drug related AEs, death or discontinuation due to an AE was comparable between groups.

An integrated body of evidence suggests that 200 mg every 3 weeks (Q3W) is expected to provide similar response to 2 mg/kg Q3W, 10 mg/kg Q3W and 10 mg/kg every 2 weeks (Q2W). Previously, a flat pembrolizumab exposure-response relationship for efficacy and safety has been found in subjects with melanoma in the range of doses between 2 mg/kg and 10 mg/kg. Exposures for 200 mg Q3W are expected to lie within this range and

will be close to those obtained with 2 mg/kg Q3W dose. 2 mg/kg Q3W is the approved dose for metastatic melanoma in the US.

A population PK model, which characterized the influence of body weight and other patient covariates on exposure, has been developed using available data from 1139 subjects from Keynote 001 (cut-off date of 18-April-2014) and Keynote 002 (cut-off date of 12-May-2014), of which the majority (94.6% (N=1077)) were patients with advanced melanoma. The PK profile of pembrolizumab is consistent with that of other humanized monoclonal antibodies, which typically have a low clearance and a limited volume of distribution. The distribution of exposures from the 200 mg fixed dose are predicted to considerably overlap those obtained with the 2 mg/kg dose and importantly will maintain individual patient exposures within the exposure range established in melanoma as associated with maximal clinical response. The slight increase in PK variability predicted for the fixed dose relative to weight-based dosing is not expected to be clinically important given that the range of individual exposures is well contained within the range of exposures shown in the melanoma studies of 2 and 10 mg/kg to provide similar efficacy and safety.

efficacy and safety as observed in subjects with melanoma can be expected, as the anti-tumor effect of pembrolizumab is driven through immune system activation rather than through a direct interaction with tumor cells, rendering it independent of the specific tumor type. In addition, available pharmacokinetic (PK) results in subjects with melanoma, NSCLC, and other solid tumor types support a lack of meaningful difference in pharmacokinetic exposures obtained at tested doses among tumor types. Thus the 200 mg Q3W fixed dose regimen is considered an appropriate fixed dose for other solid tumor indications as well.

#### **4.2.3 Translational Rationale**

The micro-environmental changes responsible for resistance to PD-1/PD-L1 blockade are incompletely understood. We will evaluate baseline tissue (archival or freshly obtained) for evidence of factors that may correlate with acquired resistance/suboptimal benefit as related to the immune microenvironment/tumor inflammation/IDO.

HNSCC is a disease with oftentimes biopsy accessible tumors, and baseline biopsies are optional (if archival tissue is available) or mandatory if no archival tissue is available.

Core biopsies (3-5 cores) will be obtained at baseline as indicated (see above/eligibility). An on treatment biopsy at 2-4 weeks on treatment will considered / is optional and dependent on ability to safely biopsy the tumor. Also in patients who have benefit and subsequently progress (acquired resistance) a biopsy may be considered.

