## 2.2 Trial Diagram

Recurrent/metastatic head and neck cancer with prior/ongoing anti-PD-1/anti-PD-L1 treatment

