### 3.3 Exploratory/Translational Objectives

- (1) Interferon-gamma Gene Expression Profile (GEP) (*Seiwert ASCO 2015, Ribas ASCO 2015*) and evaluation of RR, PFS, and OS in GEP positive and GEP negative patients.
- (2) Determine the micro-environment that underlies resistance/suboptimal treatment
  - a) underlying degree of tumor inflammation
  - b) Baseline PD-L1 expression
  - d) Determine underlying Interferon Gamma signature
- (3) Assess underlying mutational burden (*Snyder 2014*)

**Preclinical hypothesis:** IDO1 inhibition will alter the micro-environment to a be “more T-cell inflamed” and make tumors amenable to benefit from anti-PD-1 treatment (when given concurrently with IDO1 inhibition). Hence we will evaluate tumors, with prior response exhibiting acquired resistance as well as tumors with minor/suboptimal benefit from prior PD-1/PD-L1 therapy for evidence (at baseline) of suboptimal immune microenvironmental conditions.

Protocol #: UC IRB17-1539

Version Date: 04/24/2019

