### 4.2.4.2 Biomarker Research

In an effort to identify those patients who may be more likely to respond to pembrolizumab, baseline tumor samples will be evaluated for PD-L1 expression as well as other markers using an IHC or IF assay. This work will be done retrospectively.

Furthermore, patient samples will be analyzed retrospectively for GEP scoring using the Nanostring platform.

Based on data from hundreds of patients in numerous pembrolizumab studies in multiple cancer types, these biomarkers may potentially be predictive of patient benefiting from adjuvant pembrolizumab. The purpose of this trial is to assess whether potential benefit from adjuvant therapy is also related to PD-L1 and/or GEP biomarkers.

A key question of this study is whether IDO inhibition combined with PD-1 inhibition is more effective in PD-L1 expressing / GEP positive tumors or whether this combination is able to overcome the less inflamed phenotype and lead to a response in PD-L1 negative/GEP low patients.

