## **5.0 METHODOLOGY**

### **5.1 Entry Criteria / Eligibility**

#### **5.1.1 Diagnosis/Condition for Entry into the Trial**

#### **5.1.2 Subject Inclusion Criteria**

In order to be eligible for participation in this trial, the subject must fulfill the following entry criteria:

1. Patients must have histologically confirmed squamous cell carcinoma of the head and neck (unresectable and not amenable to curative intent therapy)
2. Meet criteria for either the Acquired Resistance OR the Suboptimal Benefit Cohort
  - a. **Acquired Resistance is defined as (i and ii must both be met):**
    - i. **Prior *benefit* from anti-PD-1/PD-L1 therapy defined as a) prior response, *and/or* b)  $\geq 5$  months of stable disease (SD). Intervening therapies are allowed.**
    - ii. **Progressive Disease (PD) on recent scans**
  - b. **Suboptimal Benefit is defined as (i and ii must both be met):**
    - i. **Prolonged stable disease  $\geq 5$  months OR Suboptimal response ( $>10\%$  &  $<50\%$  shrinkage per RECIST at any evaluation timepoint)**
    - ii. **Ongoing stable disease on recent scans**
    - iii. **Last treatment with an anti-PD-1/PD-L1 agent within 6 weeks prior to starting protocol treatment**
3. Archival tissue for PD-L1 staining (alternatively a new biopsy (core) at baseline can be used). A minimum of 10 slides is required (unless approval from the PI is obtained)
4. Measurable disease per RECIST 1.1.
5. Known HPV status
6. ECOG performance status 0 or 1
7. Be willing and able to provide written informed consent/assent for the trial.
8. Be  $\geq 18$  years of age on day of signing informed consent.
9. Demonstrate reasonable organ function as defined in
10. Table 1, all screening labs should be performed within 10 days of treatment initiation.

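### Cohort 1 acquired-resistance findings under objective 3.3(2) can rest on tissue taken before anti-PD-1/PD-L1 exposure, and the sections on tissue source conflict

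*Combined protocol and SAP*

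**What the plan says.** Objective 3.3(2) is to "Determine the micro-environment that underlies resistance/suboptimal treatment", and the hypothesis below it examines tumours from both cohorts "for evidence (at baseline) of suboptimal immune microenvironmental conditions". The trial diagram (2.2) describes the population as "Recurrent/metastatic head and neck cancer with prior/ongoing anti-PD-1/anti-PD-L1 treatment", so every patient has met this drug class before study baseline.

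The rules on tissue stand in four places:

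- **5.1.2, criterion 3** accepts "Archival tissue for PD-L1 staining (alternatively a new biopsy (core) at baseline can be used"). The only further condition is quantity: "A minimum of 10 slides is required (unless approval from the PI is obtained").
- **4.2.3** treats the two sources as one category: "We will evaluate baseline tissue (archival or freshly obtained) for evidence of factors that may correlate with acquired resistance/suboptimal benefit". On fresh tissue it says that "baseline biopsies are optional (if archival tissue is available) or mandatory if no archival tissue is available". The on-treatment biopsy is optional, and one at later progression is discretionary.
- **7.1.2.6, 7.2 and 7.2.8.1** place collection before curative-intent therapy. Section 7.1.2.6 names the original tumour, and 7.2.8.1 applies the rule to all patients.
- **6.1, footnote 1** speaks of a fresh biopsy/FNA requirement that the PI may waive in extenuating circumstances. The row that it belongs to is not legible in the text available.

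Section 4.2.4.2 uses baseline samples to ask whether the combination works mainly in PD-L1-expressing or GEP-positive tumours, or can also "lead to a response in PD-L1 negative/GEP low patients".

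**The concern.** Acquired resistance develops during or after exposure. To be in Cohort 1, a patient must first have benefited from anti-PD-1/PD-L1 therapy (a response, or at least 5 months of stable disease) and then have progressed. Tissue taken before that therapy shows the tumour as it was when it was about to benefit. If such tissue is entered as baseline tissue and read as evidence on resistance, the label is wrong. If it is pooled with tissue taken after progression, any acquired feature is diluted.

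At stake is the reading of objective 3.3(2) in a cohort of at most 15. Without collection dates set against exposure, nobody could tell afterwards how many specimens bear on the question.

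**Working it through.** **1. The plan's own figures.** The plan gives no figure on tissue timing. Its only design figures are those of the Simon design in 8.1: stop after 10 patients with no response, otherwise go to 15 and reject with 2 or more responses. The rejection probability is

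P(reject) = P(Bin(15, p) ≥ 2) − P(Bin(10, p) = 0) × P(Bin(5, p) ≥ 2).

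- p = 0.03: 0.0730 − 0.7374 × 0.0085 = 0.0667 (stated 0.0667).
- p = 0.20: 0.8329 − 0.1074 × 0.2627 = 0.8047 (stated 80%).

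Both reproduce. Tissue timing does not enter them, so the primary endpoint is untouched.

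**2. The tissue rules side by side.**

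| Section | Source accepted or called for | Timing relative to anti-PD-1/PD-L1 |
|---|---|---|
| 5.1.2, criterion 3 | archival, or new core | not stated |
| 4.2.3 | archival or fresh, pooled as baseline tissue | not stated |
| 7.1.2.6, 7.2, 7.2.8.1 | tissue from before curative-intent therapy | ordinarily before exposure |
| 6.1, footnote 1 | fresh biopsy/FNA, waivable | after exposure, if it means a baseline sample |

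The third row rests on an inference: in recurrent or metastatic disease, tissue from before curative-intent therapy will usually be older than the first anti-PD-1/PD-L1 dose. No row requires archival tissue to post-date exposure, and the third and fourth cannot both be the default.

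**3. What pooling does in Cohort 1.** Let a marker have mean m in tissue taken before exposure and m + d after progression, where d is the acquired change. If a share a of specimens predates exposure, and timing is unrelated to anything else, the pooled mean is

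a × m + (1 − a) × (m + d) = m + (1 − a) × d.

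The pooled data therefore show (1 − a) of the acquired change. The documents do not give a, so the whole range is shown. The specimen columns are 15 × (1 − a) for a full cohort and 10 × (1 − a) for one stopped after stage 1, if every patient supplies one specimen.

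| a (assumed) | Acquired change retained | Of 15 | Of 10 |
|---|---|---|---|
| 0% | 100% | 15 | 10 |
| 25% | 75% | 11.25 | 7.5 |
| 50% | 50% | 7.5 | 5 |
| 75% | 25% | 3.75 | 2.5 |
| 100% | 0% | 0 | 0 |

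If 7.1.2.6, 7.2 and 7.2.8.1 were followed literally, a would lie towards the bottom of the table. If footnote 1 describes the default, it would lie towards the top.

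**4. Cohort 2 and the PD-L1/GEP question.** Cohort 2 is defined by suboptimal benefit with stable disease continuing. Features present before treatment could explain that, so step 3 does not carry over. Section 4.2.4.2 asks whether marker status goes with response to the combination. Older tissue can contribute to that answer, though its status may differ from the status at entry.

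**The case against.** The strongest reply is that these are exploratory, descriptive analyses. Section 8.1 contains no biomarker analysis, 7.2.2 calls the IHC results descriptive, and no comparison between cohorts is planned. Accepting archival tissue spares patients a biopsy and looks like a deliberate trade-off. Section 4.2.3 also words its aim partly as a search for correlates, to which pre-treatment tissue can contribute. All of this stands. It limits the importance of the point and is the reason for keeping the earlier specimens. It does not make a pre-exposure specimen evidence of an acquired change.

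It may also be said that footnote 1 makes fresh tissue the default, or that the curative-intent wording was not meant for this population, since criterion 1 requires disease not amenable to curative-intent therapy. Either may be so, but the text does not settle it, and 4.2.3 and 5.1.2 would still lack a timing condition.

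Three stronger readings are tempting and are not supported:

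- **That mixed timing could reverse the direction of a finding.** Under the model above the retained share 1 − a is never negative, so the result is attenuation. Reversal would need timing to be linked to another factor, and the documents give no evidence of that.
- **That earlier tissue is useless in both cohorts and for 4.2.4.2.** The argument from acquired change belongs to Cohort 1 only.
- **That the plan has no rule on tissue timing.** It has one in three sections, but that rule points to tissue from before curative-intent therapy.

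**Conclusion.** The point holds for Cohort 1 and objective 3.3(2). As written, the plan allows tissue from before exposure to be counted as resistance tissue, and in three sections it calls for tissue that would ordinarily be of that kind. The loss is proportional to the share of such specimens, which the documents leave open between 0% and 100%. The conclusion assumes that tissue from before curative-intent therapy usually predates anti-PD-1/PD-L1 therapy here. The proportional loss also assumes that specimen timing is otherwise unrelated to the marker. Response rate, survival and safety analyses are unaffected. This is an inexpensive improvement to an exploratory objective, not a flaw in the trial's main design.

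**What to change.** 1. Reconcile 4.2.3 and 5.1.2 (criterion 3), footnote 1 of 6.1, and 7.1.2.6, 7.2 and 7.2.8.1, so that one rule states which tissue is collected.
2. Request the most recent existing specimen.
3. Record its collection date against the first and last anti-PD-1/PD-L1 dose and the date of progression. Define which progression is meant, because Cohort 1 allows intervening therapies and refers only to recent scans.
4. For Cohort 1, base acquired-resistance statements under 3.3(2) on specimens taken at or after progression. Report earlier specimens separately as pre-treatment features.
5. For Cohort 2 and the PD-L1/GEP analyses of 4.2.4.2, keep all specimens and report results by specimen timing.
6. State the number of specimens in each timing group with every result.

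The cost is a few date fields, analysis wording and an amendment to the conflicting sections. No additional biopsy is required. The real price is a smaller Cohort 1 resistance set, possibly a very small one or none, in which case the report should say that the acquired-resistance part of 3.3(2) could not be addressed.
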